This investigation does not involve a novel CI or a modification of an existing implantable device. The CIs to be used in this study are physically and technologically unchanged and have current FDA approval (Ultra MS: Model# CI-1600-04, FDA PMA Approval Number P960058/S117; Ultra Slim J: Model# CI-1600-05, FDA PMA Approval Number P960058/S121). Utilization of the device in the diagnosis and treatment of disease (i.e., hearing loss) is also unchanged and consistent with existing FDA-approved indications.

ECochG systems themselves are not novel and have been in clinical use for many years. ECochG devices are FDA-cleared Class II devices. An FDA 510(k) clearance letter is provided (See Appendix). Use of ECochG for the purposes described here is consistent with indications covered under this FDA 510(k) clearance.

The objective of this study is to learn about how ECochG-based observations during conventional CI surgery can improve outcomes compared to the standard-of-care technique of blind electrode insertion. Two clinically relevant outcomes will be considered: post-operative electrode location (i.e., correct electrode placement within the scala tympani) and hearing performance (i.e., postoperative audiometric thresholds in clinic).

Significance

Compared with previous relevant work, whereby ECochG was recorded **near** the cochlea **before** and **after** CI electrode insertion, recording ECochG from the vantage point of the CI's apical electrode **within** the cochlea **during** CI electrode insertion has the advantage of closer proximity to the ECochG signal generators (i.e., cochlear hair cells and the acoustic nerve). This approach has been shown to result in larger amplitude recording, and, thereby, more immediate feedback to the surgeon should these potentials change. An added advantage of this method is that it does not involve any change to the CI device itself, to the way the device is used, or to the surgical technique to place the device.

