The potential utility of ECochG during CI is illustrated by the following scenario: if the CI electrode touches the delicate structures of the cochlea (i.e., the basilar membrane or the spiral ligament) during insertion, the ECochG potentials become smaller in amplitude. With a real-time measurement system used during electrode insertion, decrease in ECochG potentials could be detected, and the surgeon could more purposely employ their modifications to insertion technique such as changing the insertion angle to avoid trauma or translocation.

Use of intra-cochlear electrodes for ECochG offers an additional capability of observing potentials post-operatively in the clinic. ECochG allows an objective method of monitoring hearing at regular intervals over the early post-operative period and may give insights into hearing outcomes.

Study Design

A prospective, randomized, multi-center controlled study design will be used in this study. The total study duration will be up to two years. This study will be conducted in agreement with the Internal Review Board (IRB). The study will be registered through Clinical Trials.gov (account created; registration pending IRB approval).

Outcome Measures

The post-operative outcome measures of this study will be (1) the CI electrode's scalar position as indicated by post-operative computed tomography (CT) and (2) post-operative hearing performance. Following the clinical convention, the surgeon will pre-operatively select the type of CI electrode (i.e., the MidScala electrode or the SlimJ electrode) that they would like to use during surgery. As detailed below, the patient will then be randomized to "audible ECochG signal off" or "audible ECochG signal on."

Hypotheses

The hypotheses of this study are that:

- (1) Changes in the ECochG signal observed during CI electrode insertion will correlate with insertion position outcomes as indicated by post-operative CT scan.
- (2) Participants randomized to "ECochG audible response on" will demonstrate a significantly lower rate of scalar dislocation compared to participants randomized to "ECochG audible response off."
- (3) Changes in the ECochG signal during CI electrode insertion will correlate with post-operative audiogram.
- (4) Post-operatively, changes in the ECochG *signal over time in clinic* will correlate with changes observed *over time* in post-operative audiograms.

Participants

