Block randomization is statistical strategy to prevent unequal numbers of participants from being randomized to one arm vs the other (here, audible signal "on" versus audible signal "off"). For example, using a random number generator set to individually assign 100 participants to one of two groups, there is no assurance that an equal numbers of study participants would end up in the "audible signal on" group, resulting in an unbalanced overall sample, despite randomization of each participant.

Using a block approach, the total sample is divided into smaller blocks and randomization is performed within each block with the rule that the number of allocations is balanced within that block. In our study, although each institution will likely only contribute about 40 participants, we have designed a randomization schedule to allow for 100 participants to be run for each program. This sample of 100 was divided into 50 blocks of two participants; the two participants are randomized ensuring that one goes into the "signal off" group and one goes to the "signal on" group.

Power Analysis

To ensure that our study is appropriately powered to detect a significant difference in the primary outcomes measures, we performed a power analysis with the assistance of a biostatistician. Post-operative CT-based indication of scalar position is treated as a dichotomous variable (i.e., either in the scala tympani or in the scala vestibuli); post-operative hearing outcomes are treated as a continuous variable.

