Scalar Dislocation: Preliminary data indicates that the current state of CI electrode dislocation from the scala tympani to the scala vestibuli is approximately 35% (or, a “successful” scala tympani position is achieved at a rate of 65%). For participants randomized to “ECochG audible signal on,” our expectation, driven by preliminary data, is to decrease the rate of scalar dislocation to approximately 15% (or, a “successful” scala tympani position rate of 85%). Setting the alpha error rate at 2.5%, a total sample size of 192 participants, or 96 participants in each of the two randomization groups, was determined using a Fischer exact test. If we permit a 5% error rate, the total sample size drops to 162 patients (81 randomized to audible signal “on”; 81 randomized to signal “off”). While these numbers of participants are higher than would be possible to achieve at our site alone in an average two-year period, through a coordinated effort to pool multi-center data, it will be easily achievable.

Secondary Planned Analysis

Electrode Type: As detailed above, once a participant is enrolled in the study, the surgeon will select which of two CI electrodes are most appropriate. A secondary analysis comparing scalar position and hearing preservation outcomes will be performed (i.e., four total between-group analyses) between the two electrode groups.

Pediatric Participants: This study will include both adult and pediatric participants. A secondary analysis comparing scalar position and hearing outcomes between adult and pediatric participants will be performed (again, four total between-group analyses).

Regression Analysis: To model the influence of “ECochG on” on the primary outcome measures in the context of participant age group and electrode choice, two regression analyses will be performed – one for the outcome measure of scalar position and one for hearing outcomes.

Hospital Effect Analysis: To determine if there is a meaningful difference in outcome measures across the different participating hospital settings, a secondary analysis will be performed as well.

Safeguarding of Protected Health Information (PHI)

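### Hearing is treated as a primary outcome, yet no hypothesis compares it between the arms, and the dislocation test level that depends on its status is left open

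*Protocol*

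**What the plan says.** - **Objectives.** The study is to learn how ECochG observations "can improve outcomes compared to the standard-of-care technique of blind electrode insertion". The same paragraph continues: "Two clinically relevant outcomes will be considered: post-operative electrode location", and names hearing performance as the second outcome. Outcome Measures lists the same two without ranking them.
- **Hypotheses.** Hypothesis 2 says that signal-on participants "will demonstrate a significantly lower rate of scalar dislocation compared to participants randomized to" the signal-off arm. Hypothesis 1 relates the ECochG signal to electrode position on CT. Hypotheses 3 and 4 relate it to the audiogram. None of these three compares the arms.
- **Power Analysis.** The study is to be "appropriately powered to detect a significant difference in the primary outcomes measures", in the plural. The next sentence treats scalar position as dichotomous and says that "post-operative hearing outcomes are treated as a continuous variable".
- **Scalar Dislocation.** The calculation reads "Setting the alpha error rate at 2.5%, a total sample size of 192 participants", by Fisher's exact test for 35% against 15%. It adds that a 5% error rate would need 162. Participants adopts 192. There is no calculation for hearing.
- **Secondary Planned Analysis, Regression Analysis.** The effect of having the signal on is to be modelled for the primary outcome measures in two regressions, "one for the outcome measure of scalar position and one for hearing outcomes".

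**The concern.** The protocol gives hearing two different ranks. Objectives, Power Analysis and the wording of the regression paragraph make it a primary outcome on which the arms are to be compared. The hypotheses contain no such comparison, and the one analysis that plainly estimates the arm effect on hearing sits under a secondary heading. A correlation between the ECochG signal and the audiogram cannot stand in for it: it can be strong whether or not giving the surgeon the signal improves hearing.

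Two things depend on the rank. One is whether a hearing benefit, which is half of the stated objective, can be claimed as a confirmatory result. The other is the level at which dislocation should be tested. With one confirmatory arm comparison, dislocation can have the whole 5%. With two, the 5% must be shared or ordered. Testing both at 5% would allow a family-wise error of up to 10%. The protocol settles neither the rank nor the level, and a choice made after the results are known would carry little weight.

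**Working it through.** **Inputs from the protocol (Scalar Dislocation).** Control dislocation rate 0.35; signal-on rate 0.15; Fisher's exact test; 96 per arm (192) at alpha 2.5%; 81 per arm (162) at alpha 5%.

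**Assumptions.** Power and sidedness are not stated. I take 80% power and two-sided tests first, then look at one-sided tests.

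**Formula.** Power = sum over all (x1, x2) of Bin(x1; n, 0.35) × Bin(x2; n, 0.15), counting only the tables whose Fisher p-value is at most alpha. The two-sided p-value adds the hypergeometric probabilities, with the margins fixed, of all tables no more probable than the one observed.

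**Step 1: reproduce the stated totals.** Two-sided, the smallest n per arm that holds 80% power is 95 at 2.5% (total 190, against 192 stated) and 81 at 5% (total 162, exactly as stated). Both totals reproduce, to within one participant per arm.

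**Step 2: exact power at the stated sizes.**

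| n per arm | alpha | two-sided | one-sided |
|---|---|---|---|
| 96 | 2.5% | 80.7% | 87.5% |
| 96 | 5% | 87.5% | 92.7% |
| 81 | 2.5% | 71.8% | 80.2% |
| 81 | 5% | 80.2% | 87.8% |

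On the two-sided reading, the 2.5% level is consistent with 5% / 2, one half for each of two primary tests. On a one-sided reading the two stated pairs also agree with each other, at 87.5% and 87.8%, and 2.5% is then simply the counterpart of two-sided 5%.

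**Step 3: what the choice of level is worth at 192.** Two-sided: 0.8746 − 0.8070 = 0.0676, or 6.8 percentage points of power for dislocation.

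**Step 4: Holm with hearing as the second test.** Dislocation is rejected if its p is at most 0.025, or if its p is at most 0.05 and the hearing p is at most 0.025. Power is therefore 0.8070 plus the probability that the dislocation p lies between 0.025 and 0.05 while hearing is significant at 0.025. That addition lies between 0 and 0.0676, so power is between 80.7% and 87.5%, with family-wise error at most 5%. Testing both at 5% without adjustment would give 1 − 0.95² = 9.75% if the tests were independent, and at most 10% otherwise.

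**Step 5: hearing.** The protocol gives no standard deviation or target difference, so no power can be computed. As a guide only, with 96 per arm, complete data, a normal approximation and 80% power, the detectable standardised difference is (2.241 + 0.842) × √(2/96) = 0.44 SD at two-sided 2.5%, and (1.960 + 0.842) × √(2/96) = 0.40 SD at two-sided 5%. The endpoint is not singled out either: eight frequencies are to be reported individually, and there are three post-operative visits, so 8 × 3 = 24 frequency-by-visit results are available.

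**The case against.** The best reply is that the hearing comparison is planned and only its label is untidy. The objective is worded softly, the list of hypotheses does not claim to be complete, Power Analysis implies an arm difference in hearing, and the regression estimates one. The four between-group analyses by electrode type and by age group are ambiguous and might include arm contrasts on hearing. The final test level and any multiplicity procedure may be in a statistical analysis plan that is not at hand.

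Much of this stands, and it rules out several stronger readings that a reader might infer:

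- *That dislocation will be tested at a fixed 2.5%.* The protocol uses 2.5% to size the study, mentions 5% as an alternative, and states no final test level.
- *That power is therefore being lost for nothing.* If dislocation is tested at two-sided 5% with 192, power is already 87.5%. On the one-sided reading nothing is given up either.
- *That 2.5% is proven to be a Bonferroni half.* The protocol mentions no split. The figures are consistent with one, but only under assumed 80% power and two-sided tests.
- *That hearing is never compared between arms.* It is, in the regression.

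What the reply does not remove is the conflict over rank. Calling hearing primary in Power Analysis, leaving it out of the only arm hypothesis and heading its explicit arm model secondary are all statements in the protocol itself. The between-group analyses, whatever they contain, are also listed as secondary.

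**Conclusion.** The point holds as an inconsistency that should be resolved before analysis. Hearing's primary status is not carried into the hypotheses or into an arm comparison of primary rank, and the dislocation test level, which depends on that status, is open between 2.5% and 5%. At the adopted 192, with 35% against 15% and two-sided Fisher tests, the open level is worth 6.8 points of power (80.7% against 87.5%). Those rates and the test are the protocol's; two-sidedness, and the 80% power used to reproduce its totals, are assumptions. The inconsistency over hearing does not depend on either assumption.

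**What to change.** Keep 192 and choose one of the following before any comparison by arm is made.

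(a) **Hearing by arm is not confirmatory.** Call it secondary in Power Analysis and in the regression paragraph, and state that dislocation is tested at two-sided 5%. Power for 35% against 15% is then 87.5%. The cost is that no confirmatory claim about hearing can be made.

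(b) **Hearing by arm is confirmatory.** Add a hypothesis that compares hearing between the randomised arms, naming one threshold measure and one visit from those already collected. Test it with Hypothesis 2 by Holm at an overall two-sided 5%: the smaller p-value against 2.5% and, if that is significant, the other against 5%. Dislocation power is then between 80.7% and 87.5%. State that the sample size was derived for dislocation only. The cost is a confirmatory test for which no power has been shown.

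In either case, state the sidedness and the power behind 192. Both options change only the text on hypotheses, power and analysis; neither needs more patients, visits or measurements.

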- a) Ensure that no cerumen or surgical preparation fluid is in the external ear canal. Place the ear piece in the external ear canal and fold the pinna forward, as in the conventional procedure.
- b) Enter the pre-op audiogram into the software.
- c) Normal CI surgical approach. A conventional round window or extended round window entry into the cochlea is prepared.
- d) Measure ECochG in response to a 500 Hz tone burst stimulus, at 110 dB SPL, during insertion of the CI electrode and after insertion of the CI electrode. Figure 2 schematically depicts the intraoperative set-up. Figure 3 shows the non-invasive surface electrode and earphone array used in ECochG. Figure 4 shows the enclosure box and monitoring screen.
 - i) For participants randomized to Arm 1 of the study, the surgeon will perform CI electrode insertion without ECochG feedback.
 - ii) For participants randomized to Arm 2 of the study, the surgeon will make insertion modifications as appropriate in response to ECochG feedback.

3) Initial CI Activation Visit (3-5 weeks after surgery)

- a) Audio Assessment
 - i) Unaided pure tone audiometry in the implanted and the unimplanted ear
 - ii) Bone-conduction thresholds when possible, depending on the patient's residual hearing status

- iii) For pediatric patients, unaided audiometric data may be collected as tolerated, across different visits, to accommodate the unique challenges of hearing assessment of young children.
- b) **Measure ECochG responses in clinic** (to coincide with audiology, +/- 1 week)
 - i) 125-2000 Hz (frequency scan)
 - ii) At an acoustic intensity level at or below their comfortable level through an insert earphone
 - iii) Directly through the CI
- c) Post-Op CT scan to identify CI electrode scalar location
 - i) Obtain scan within one month following surgery
 - ii) Patient identifiers removed from CT scan data and sent to collaborators in DICOM format for analysis (See Appendix 1).

4) Approximately 3 Month Visit

- a) Audio Assessment
 - i) Pure tone unaided audiology in the implanted and the unimplanted ear
 - ii) Bone-conduction thresholds when possible, depending on the patient's residual hearing status
- b) Measure ECochG responses in clinic (to coincide with audiology, +/- 1 week)
 - i) 125-2000 Hz (frequency scan)
 - ii) At an acoustic intensity level at or below their comfortable level through an insert earphone
 - iii) Directly through the CI

5) Approximately 12 Month Visit

- a) Audio Assessment

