 - i) Pure tone unaided audiology in the implanted and the unimplanted ear
 - ii) Bone-conduction thresholds as appropriate
- b) Measure ECochG responses in clinic (to coincide with audiology, +/- 1 week)
 - i) 125-2000 Hz frequency scan
 - ii) At an acoustic intensity level at or below their comfortable level through an insert earphone
 - iii) Directly through the CI

Detailed description of measurements and procedure

Pure tone and bone-conduction audiology

Pure tone audiology will be performed following the conventional, routine protocol currently in place for determining CI candidacy. Where possible, pure tone thresholds will be established in the implanted ear for 125, 250, 500, 750, 1000, 1500, 2000, 3000, 4000, 6000, and 8000 Hz. Testing will be conducted using insert earphones, and where indicated, the contralateral ear will be masked. Both the implanted and the non-implanted ear will be measured. If clinically appropriate, bone-conduction testing will be performed as well following conventional practices. For young children in our cohort, for whom

hearing testing can be uniquely challenging, thresholds obtained across more than one visit will be permitted and thresholds may be estimated base on auditory brainstem response (ABR) testing.

In line with the Minimum Reporting Standards for Adult Cochlear Implantation recommendations [11], in patients with functionally relevant pre-operative low frequency pure tone averages (125, 250, 500 Hz) < 80 dB HL, post-operative residual hearing will be reported. Each frequency will be reported individually (125, 250, 500, 1000, 1500, 2000, 4000, and 8000 Hz) rather than as a pure tone average.

Electrocotileography

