In the operating room, a 500 Hz tone burst will be presented to the participant at a 110 dB SPL through an insert earphone in the external auditory canal. This acoustic stimulus will provoke movements of remaining inner and outer cochlear hair cells and evoke a response from the auditory nerve. Tone burst stimuli at 500 Hz have been shown to produce the largest amplitude ECochG response, therefore, will be used as the default stimulus here. The resulting cochlear potentials will be recorded using the recording electrode from the apical aspect of the CI electrode. By averaging the recorded signal synchronized with stimulus delivery, the responses can be reinforced while unsynchronized noise will average out. For a more detailed description of ECochG measurements, please see [10]. This utilization is consistent with indications covered under this FDA 510(k) clearance.

Intra-operative preparation

The insert earphone will be placed in the external ear canal after cerumen removal. The ear canal will be surgically prepared, followed by suctioning of prep fluid. Following the conventional technique, the measurement ear will be folded forward and taped. The surgery will proceed following the standard-of-care practice consisting of a cortical mastoidectomy, a facial recess (posterior tympanotomy), and preparation of intracochlear access via the round window or an extended round window approach. Before the CI electrode will be inserted, the headpiece will be connected to the implant, and the ECochG software will be triggered to begin the ECochG recordings. Figure 2 depicts a schematic of the measurement system setup. Figure 3 shows an example of the noninvasive surface electrode and earphone array. Figure 4 shows the monitor and unit through which the ECochG is observed and recorded.

To facilitate correlation of changes in ECochG potentials during CI electrode insertion and surgical events that ultimately relate to trauma within the cochlea, the surgeon will verbally indicate the progress of electrode insertion (e.g., “at the round window,” “at the first marker on the electrode,” “at the last marker on the electrode”), which will be recorded in the software by an assistant and synched with the ECochG signals.

Post-operative ECochG

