For post-operative ECochG measurements in the clinic, the setup depicted in Figure 3 will be utilized. For this testing, the external component of the CI will be temporarily removed (equivalent to simply taking off a hearing aid) and replaced with an external head coil component (physically identical to the CI's external head coil) that allows for ECochG measurement. After connecting the head piece, a frequency scan from 125-2000 Hz will be presented to the participant at an acoustic intensity level at or below their comfortable listening level through an insert earphone in the external auditory canal. After measurements are collected, the participant's own external component will be put back in place. This measurement takes up to 5 minutes and does not require active participation of the participant.

CT Scan

A single post-operative CT scan will be conducted to identify the electrode's scalar location. A post-operative CT scan is often performed as a part of the regular clinical routine in patients for whom more information about the CI electrode location is needed. The post-operative CT will be collected per parameters outlined in Appendix 1.

Risks

The chief risks associated with this study are those inherent to CI surgery itself. The use of intraoperative ECochG has been well-demonstrated to pose no added patient risks, but may, as discussed above, provide an important benefit. Participation in this study will involve the following specific considerations:

1. *Increased surgical time:* The ECochG measurement procedure adds up to 5-15 minutes to the procedure. During this added procedure time, the Anesthesia team will closely monitor the patient. If there are any concerns at any time, the study activity will be ceased.
2. *Post-operative CT scan:* Associated radiation exposure.

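### Hypothesis 4 correlates two measures whose sound crosses the same recently operated middle ear, so a positive result cannot by itself be read as cochlear change

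*Protocol*

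**What the plan says.** Under Hypotheses, the fourth hypothesis reads: "Post-operatively, changes in the ECochG *signal over time in clinic* will correlate with changes observed *over time* in post-operative audiograms".

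- **Audiogram.** Pure tone and bone-conduction audiology says: "Testing will be conducted using insert earphones, and where indicated, the contralateral ear will be masked".
- **Clinic ECochG.** Post-operative ECochG has a frequency scan presented "at an acoustic intensity level at or below their comfortable listening level through an insert earphone in the external auditory canal". The recording is made through the implant; under Significance: "Use of intra-cochlear electrodes for ECochG offers an additional capability of observing potentials post-operatively in the clinic". So only the stimulus side of the ECochG measurement crosses the middle ear.
- **Surgery.** Intra-operative preparation describes "a cortical mastoidectomy, a facial recess (posterior tympanotomy), and preparation of intracochlear access via the round window or an extended round window approach".
- **Timing.** Protocol timeline puts the first post-operative measurements at activation, 3-5 weeks after surgery, and repeats them at about 3 and 12 months.
- **Bone conduction.** It is listed at all three visits, but conditionally. At activation and 3 months the entry is "Bone-conduction thresholds when possible, depending on the patient's residual hearing status"; at 12 months it is "Bone-conduction thresholds as appropriate".

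Neither Hypotheses nor Secondary Planned Analysis ties bone conduction or the air-bone gap to Hypothesis 4. The exclusion criteria on middle-ear disease and earlier ear surgery concern the state before the operation only.

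**The concern.** An air-conduction threshold is the sum of cochlear loss and any loss in the canal and middle ear. The ECochG amplitude depends on the sound that reaches the hair cells, and that sound has crossed the same canal and middle ear. If conductive loss after surgery clears between two visits, the threshold improves and, at a constant stimulus level, the ECochG grows. The two changes then correlate in the expected direction even if the cochlea has not altered.

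What is at stake is the meaning of a positive Hypothesis 4. The background section on electrocochleography attributes the signal to hair cells and auditory nerve, and Significance presents post-operative ECochG as an objective way to monitor hearing. A reader will tend to take a positive correlation as evidence that clinic ECochG tracks cochlear status. The analysis as described cannot separate that explanation from a shared conductive shift, although the measurement that could do so is partly scheduled.

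**Working it through.** **The plan's own figure.** No expected correlation or sample size is given for Hypothesis 4. The only calculation is for dislocation (35% v 15%). It reproduces: an exact two-sided Fisher test with 96 per arm at alpha 2.5% has 80.7% power, although the target power is not stated. Nothing below depends on it.

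**Model.** Signs are set so that improvement is positive, and all terms are in dB:

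- audiogram change = C + M + e1
- ECochG change = (1 - k)M + e2

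C is cochlear change (SD sc) and M is conductive change (SD sm). The share of M offset by the comfort-set level is k. In this worst case ECochG carries no part of C. With independent terms:

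r = (1 - k)·sm² / √[(sc² + sm² + 50)·((1 - k)²·sm² + se²)]

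**Inputs, all assumptions:**

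- sc = 10 or 15 dB.
- Audiometric error SD 5 dB per visit, so the variance of a change is 2 × 5² = 50.
- se² = 50 or 200, that is 2 × 5² or 2 × 10². The larger value takes the Protocol's ±10 dB threshold accuracy as one SD per visit.
- sm = 3, 5 or 10 dB.
- ECochG moves one dB for each dB of sound reaching the cochlea.

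**Numbers for sm = 5, k = 0:**

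- Highest (sc = 10, se² = 50): 25 / √(175 × 75) = 0.22.
- Lowest (sc = 15, se² = 200): 25 / √(300 × 225) = 0.10.

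| SD of conductive change | r, constant level (k = 0) | r, half offset (k = 0.5) | r, full offset (k = 1) |
|---|---|---|---|
| 3 dB | 0.04-0.09 | 0.02-0.05 | 0 |
| 5 dB | 0.10-0.22 | 0.05-0.13 | 0 |
| 10 dB | 0.30-0.52 | 0.17-0.37 | 0 |

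The two-sided 5% critical r is 0.142 if all 192 participants supply a pair, and 0.254 at n = 60. By Fisher's z, the chance of significance is:

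- **5 dB, k = 0:** 26-86% at n = 192.
- **10 dB, k = 0:** at least 64% at n = 60 and about 99% or more at n = 192.
- **5 dB, k = 0.5:** 11-41% at n = 192.
- **10 dB, k = 0.5:** 67% or more at n = 192.
- **3 dB, k = 0:** at most 25% at n = 192, with r² below 0.01.

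**Sensitivity 1: no cochlear variation at all.** Drop sc and take SDs of 5-7 dB for the audiogram change and 5-14.1 dB for the ECochG change. At k = 0, sm = 5 gives r from 25 / √(74 × 223.8) = 0.19 to 25 / √(50 × 50) = 0.50; sm = 2 gives 0.04-0.14.

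**Sensitivity 2: ECochG tracks cochlear change one for one.** Then r = (sc² + sm²) / √[(sc² + sm² + 50)(sc² + sm² + se²)] at k = 0. With sc = 10 and se² = 50, r goes from 100/150 = 0.667 at sm = 0 to 125/175 = 0.714 at sm = 5. Over all combinations, sm = 5 adds 0.015-0.053 and sm = 10 adds 0.05-0.16. If ECochG does track the cochlea, the inflation is modest.

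**The case against.** **Hypothesis 4 claims only a correlation with audiograms.** If both measures follow the middle ear, that claim is still true. This stands: the problem lies in the cochlear reading, which the text invites but the hypothesis does not state.

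**The word audiograms need not mean air conduction alone.** Bone conduction is part of each visit's audiological assessment. This is fair, but the Protocol does not say which thresholds enter Hypothesis 4, and bone conduction will be missing in some ears.

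**The modelling belongs in a statistical analysis plan, which is not at hand.** The covariate details do. What the Protocol fixes is a hypothesis about two measures with a shared path, and a separating measurement that is optional and not linked to it.

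**The level is set by comfort, not held constant.** If comfort follows conductive loss, the effect shrinks and can vanish. This stands. But the stated rule is at or below comfort, which does not guarantee an offset, and an unrecorded change of level would itself change the ECochG.

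**Two stronger readings are tempting.** A reader might infer that middle-ear recovery will create the correlation, so that Hypothesis 4 would succeed when ECochG tracks nothing. The documents give neither size nor timing of any conductive change, and that reading needs zero cochlear tracking and a constant level. A reader might also infer that one earphone serves both tests. The documents show only the same kind of route, and thresholds in young children may be estimated from ABR.

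**Conclusion.** The shared sound path is documented for both measures, and the analysis described for Hypothesis 4 does not separate conductive from cochlear change. A positive result can therefore be inflated by middle-ear change. By how much is unknown. With no cochlear tracking and a constant level, the induced r is negligible at a conductive SD of about 3 dB, can reach significance at 5 dB and is substantial at 10 dB. It falls towards zero as the comfort-set level follows the loss, and the inflation is modest if ECochG does track the cochlea. Every SD is an assumption, and the n = 192 figures require usable pairs from every participant.

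This limits the interpretation of Hypothesis 4. It does not show that the hypothesis is false or that the correlation will be spurious. The randomised comparison of dislocation in Hypothesis 2 and the sample size of 192 are untouched.

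**What to change.** 1. Keep the air-conduction correlation as the Hypothesis 4 result, and label it as including middle-ear effects.
2. Add a supporting analysis restricted to ears and visit pairs with measurable bone conduction. Use bone-conduction change at the matched frequency, or air-conduction change adjusted for the change in air-bone gap.
3. Record the ECochG stimulus level at each clinic visit and account for it in both analyses.
4. State that a cochlear conclusion will be drawn from Hypothesis 4 only if the association holds in the supporting analysis. Report how many ears and visit pairs contribute to it.

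**Cost.** The change is to the wording of the analysis, plus one recorded value per ECochG session; no visit or test is added. Because bone conduction is conditional, the subset will be smaller and probably better-hearing, and its interval wider. That selection is why bone conduction should not replace the main Hypothesis 4 measure. Where bone conduction cannot be measured, the air-bone gap cannot be computed either, so those ears allow no adjustment and support only the labelled air-conduction result.
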